10.3.3 Collection of Pregnancy Information

Male subjects with partners who become pregnant

- The investigator will attempt to collect pregnancy information on any male subject's female partner who becomes pregnant while the male subject is in this study.
- After obtaining the necessary signed informed consent from the pregnant female partner directly, the investigator will record pregnancy information on the appropriate form and submit it to the Sponsor within 24 hours of learning of the partner's

pregnancy. The female partner will also be followed to determine the outcome of the pregnancy. Information on the status of the mother and child will be forwarded to the Sponsor. Generally, the follow-up will be no longer than 6 to 8 weeks following the estimated delivery date. Any termination of the pregnancy will be reported regardless of fetal status (presence or absence of anomalies) or indication for the procedure.

Female Subjects who become pregnant

- The investigator will collect pregnancy information on any female subject who becomes pregnant while participating in this study. The initial information will be recorded on the appropriate form and submitted to the Sponsor within 24 hours of learning of a subject's pregnancy.
- The subject will be followed to determine the outcome of the pregnancy. The investigator will collect follow-up information on the subject and the neonate and the information will be forwarded to the Sponsor. Generally, follow-up will not be required for longer than 6 to 8 weeks beyond the estimated delivery date. Any termination of pregnancy will be reported, regardless of fetal status (presence or absence of anomalies) or indication for the procedure.
- While pregnancy itself is not considered to be an AE or SAE, any pregnancy complication or elective termination of a pregnancy for medical reasons will be reported as an AE or SAE.
- A spontaneous abortion (occurring at <22 weeks gestational age) or still birth (occurring at >22 weeks gestational age) is always considered to be an SAE and will be reported as such.
- Any post-study pregnancy-related SAE considered reasonably related to the study drug by the investigator will be reported to the Sponsor as described in Section 8.4.8. While the investigator is not obligated to actively seek this information in former study subjects, he or she may learn of an SAE through spontaneous reporting.
- Any female subject who becomes pregnant while participating in the study will discontinue study drug or be withdrawn from the study.

10.4 NEURODEGENERATIVE DISEASES DIAGNOSTIC CRITERIA

Below are diagnostic criteria for neurodegenerative diseases evaluated in this study.

10.4.1 Parkinson's Disease Diagnostic Criteria

Table 9 Movement Disorder Society (MDS) Diagnostic Criteria for Clinically Established Parkinson's Disease

Parkinsonism consist of bradykinesia plus either rigidity or rest tremor, as defined below								
Bradykinesia: slowness of movement AND decrement in amplitude or speed (or progressive hesitations/halts) as movements are continued	Rigidity: velocity-independent resistance to passive movement not solely reflecting failure to relax (i.e., distinct from spasticity or paratonia)	Rest tremor: a 4- to 6-Hz tremor in the fully resting limb, which is suppressed during movement initiation						
Clinical established Parkinson's disease is defined as: Absence of absolute exclusion criteria; at least 2 supportive criteria; no 'red flags' (as defined below)								

  
 Absolute Exclusion Criteria	Red Flags	Supportive Criteria	
   
  
 • Cerebellar signs • Supranuclear gaze palsy • Established diagnosis of BVFTD • Parkinsonism restricted to the lower limbs only for >3 years • Treatment with an antidopaminergic, or with dopamine-depletion agents • Absence of response to levodopa • Sensory–cortical loss • No evidence for dopaminergic deficiency on functional imaging • Other parkinsonism-inducing condition 	 
 • Rapid deterioration of gait • Absence of motor symptom progression over 5 years • Early bulbar dysfunction • Respiratory dysfunction • Early severe autonomic failure • Early recurrent falls due to misbalance • Disproportionate anterocollis • Absence of common non-motor features of disease during >5 years • Pyramidal tract signs • Bilateral symmetric presentation 	 
 • A clear and dramatic positive response to dopaminergic therapy • Levodopa-induced dyskinesia • Documentation of resting tremor of a limb • A positive diagnostic test of either olfactory loss or cardiac sympathetic denervation on scintigraphy 	
  
			Absolute Exclusion Criteria	Red Flags	Supportive Criteria	
 • Cerebellar signs • Supranuclear gaze palsy • Established diagnosis of BVFTD • Parkinsonism restricted to the lower limbs only for >3 years • Treatment with an antidopaminergic, or with dopamine-depletion agents • Absence of response to levodopa • Sensory–cortical loss • No evidence for dopaminergic deficiency on functional imaging • Other parkinsonism-inducing condition 	
 • Rapid deterioration of gait • Absence of motor symptom progression over 5 years • Early bulbar dysfunction • Respiratory dysfunction • Early severe autonomic failure • Early recurrent falls due to misbalance • Disproportionate anterocollis • Absence of common non-motor features of disease during >5 years • Pyramidal tract signs • Bilateral symmetric presentation 	
 • A clear and dramatic positive response to dopaminergic therapy • Levodopa-induced dyskinesia • Documentation of resting tremor of a limb • A positive diagnostic test of either olfactory loss or cardiac sympathetic denervation on scintigraphy
Absolute Exclusion Criteria	Red Flags	Supportive Criteria						

 • Cerebellar signs • Supranuclear gaze palsy • Established diagnosis of BVFTD • Parkinsonism restricted to the lower limbs only for >3 years • Treatment with an antidopaminergic, or with dopamine-depletion agents • Absence of response to levodopa • Sensory–cortical loss • No evidence for dopaminergic deficiency on functional imaging • Other parkinsonism-inducing condition 	
 • Rapid deterioration of gait • Absence of motor symptom progression over 5 years • Early bulbar dysfunction • Respiratory dysfunction • Early severe autonomic failure • Early recurrent falls due to misbalance • Disproportionate anterocollis • Absence of common non-motor features of disease during >5 years • Pyramidal tract signs • Bilateral symmetric presentation 	
 • A clear and dramatic positive response to dopaminergic therapy • Levodopa-induced dyskinesia • Documentation of resting tremor of a limb • A positive diagnostic test of either olfactory loss or cardiac sympathetic denervation on scintigraphy 						

Abbreviation: BVFTD, behavioral variant frontotemporal dementia.

Source: [\(Postuma, 2015\)](#)

Table 10 Parkinson's Disease Criteria per Hoehn and Yahr (1967)

Stage	Hoehn and Yahr Scale
1	Unilateral involvement only usually with minimal or no functional disability
2	Bilateral or midline involvement without impairment of balance
3	Bilateral disease: mild to moderate disability with impaired postural reflexes; physically independent
4	Severely disabling disease; still able to walk or stand unassisted
5	Confinement to bed or wheelchair unless aided

Source: [\(Hoehn, 1967\)](#)

10.4.2 MSA Diagnostic Criteria

Division into clinically established MSA-P or MSA-C according to predominant motor syndrome

Essential features	A sporadic, progressive adult (>30 years) onset disease	
	Clinically established MSA	Clinically probable MSA
Core clinical features	
1. Autonomic dysfunction defined as (at least one is required)
 
 o Unexplained voiding difficulties with post-void urinary residual volume ≥ 100 mL o Unexplained urinary urge incontinence o Neurogenic OH ($\geq 20/10$ mmHg blood pressure drop) within 3 minutes of standing or head-up tilt test 
and at least one of
 
 1. Poorly L-dopa-responsive parkinsonism 2. Cerebellar syndrome (at least two of gait ataxia, limb ataxia, cerebellar dysarthria, or oculomotor features) 	
At least two of:
 
 1. Autonomic dysfunction defined as (at least one is required): o Unexplained voiding difficulties with post-void urinary residual volume o Unexplained urinary urge incontinence o Neurogenic OH ($\geq 20/10$ mmHg blood pressure drop) within 10 minutes of standing or head-up tilt test 
 2. Parkinsonism 3. Cerebellar syndrome (at least one of gait ataxia, limb ataxia, cerebellar dysarthria, or oculomotor features)
Supportive clinical (motor or non-motor) features	At least two	At least one ^a
MRI marker	At least one	Not required
Exclusion criteria	Absence	Absence
Supportive clinical features		
Supportive motor features	
Rapid progression within 3 years of motor onset
 
Moderate to severe postural instability within 3 years of motor onset
 
Craniocervical dystonia induced or exacerbated by L-dopa in the absence of limb dyskinesia
 
Severe speech impairment within 3 years of motor onset
 
Severe dysphagia within 3 years of motor onset
 
Unexplained Babinski sign
 
Jerky myoclonic postural or kinetic tremor
 
Postural deformities
	
Supportive non-motor features
 
Stridor
 
Inspiratory sighs
 
Cold discolored hands and feet
 
Erectile dysfunction (below age of 60 years for clinically probable MSA)
 
Pathologic laughter or crying

MRI markers of clinically established MSA		
Each affected brain region as evidenced by either atrophy or increased diffusivity counts as one MRI marker.		
For MSA-P	
 • Atrophy of: 
 o Putamen (and signal decrease on iron-sensitive sequences) o Middle cerebellar peduncle o pons o Cerebellum • "Hot cross bun" sign 	
For MSA-C	
 • Atrophy of: 
 o Putamen (and signal decrease on iron-sensitive sequences) o Infratentorial structures (pons and middle cerebellar peduncle) • "Hot cross bun" sign 	

Continued

- Increased diffusivity of:
 - Putamen
 - Middle cerebellar peduncle
- Increased diffusivity of:
 - Putamen

Exclusion criteria

Substantial and persistent beneficial response to dopaminergic medications

Unexplained anosmia on olfactory testing

Fluctuating cognition with pronounced variation in attention and alertness and early decline in visuoperceptual abilities

Recurrent visual hallucinations not induced by drugs within 3 years of disease onset

Dementia according to DSM-V within 3 years of disease onset

Downgaze supranuclear palsy or slowing of vertical saccades

Brain MRI findings suggestive of an alternative diagnosis (eg, PSP, multiple sclerosis, vascular parkinsonism, symptomatic cerebellar disease, etc.)

Documentation of an alternative condition (MSA look-alike, including genetic or symptomatic ataxia and parkinsonism) known to produce autonomic failure, ataxia, or parkinsonism and plausibly connected to the patient's symptoms

Source: [\(Wenning, 2022\)](#)

10.4.3 ALS Diagnostic Criteria

Table 11 ALS Diagnostic Criteria

Definite ALS	Presence of upper motor neuron and lower motor neuron signs in the bulbar region and at two of the other spinal regions
Probable ALS	Presence of upper motor neuron and lower motor neuron signs in at least two regions with upper motor neuron signs rostral to lower motor neuron signs
Probable ALS, laboratory results supported	Presence of upper motor neuron and lower motor neuron signs in one region with evidence by EMG of lower motor neuron involvement in another region
Possible ALS	Presence of upper motor neuron and lower motor neuron signs in one region or upper motor neuron signs in two or three regions, such as monomelic ALS, progressive bulbar palsy, and primary lateral sclerosis

ALS, amyotrophic lateral sclerosis; EMG, electromyography.

Source: [\(Brooks, 2000\)](#)

10.5 ABBREVIATIONS

Term	Description
α -syn	alpha-synucleinopathies
AE	Adverse event
ALS	Amyotrophic lateral sclerosis
AUC	Area under the curve
CFR	Code of Federal Regulations
CI	Confidence interval
C_{max}	Peak plasma concentration
CMP	Clinical Monitoring Plan
CONSORT	Consolidated Standards of Reporting Trials
CRIC	Central Retinal Image Center
CRO	Clinical Research Organization
CT	Computed tomography
CTCAE	Common Terminology Criteria for Adverse Events
CV	Coefficient of variation
DaTscan	Dopamine transport scan
ECG	Electrocardiogram
eCRF	Electronic case report form
EDC	Electronic data capture
EOS	End-of-study
ET	Early termination
FAF	Fundus autofluorescence
FDA	Food and Drug Administration
FF	Fundus fluorescence
FIH	First-in-human
FSH	Follicle-stimulating hormone
FU	Follow-up
GCP	Good Clinical Practice
geo CV	geometric coefficient of variation
GLP	Good Laboratory Practices
GMP	Good Manufacturing Practices
HED	Human equivalent dose
hERG	Human Ether-à-go-go-related gene
IB	Investigator's Brochure
ICH	International Council for Harmonisation
IND	Investigational New Drug Application
IRB	Institutional Review Board
ISR	Injection site reaction
IV	Intravenous
MedDRA	Medical Dictionary for Regulatory Activities

Term	Description
MRI	Magnetic resonance imaging
MRSD	Maximum recommended starting dose
NCI	National Cancer Institute
NOAEL	No observed adverse effect level
OCT	Optical coherence tomography
OCT-A	OCT angiography
PET	Positron emission tomography
PK	Pharmacokinetic
PROBE	Prospective Randomized Open, Blinded Endpoint
QA	Quality assurance
QC	Quality control
SAE	Serious adverse event
SAP	Statistical analysis plan
SD	Standard deviation
SMC	Safety Monitoring Committee
SoA	Schedule of activities
SOP	Standard operating procedure
SUSAR	Suspected unexpected serious adverse reaction
TDP-43	Transactive response DNA-binding protein 43
US	United States
WOCBP	Woman of childbearing potential

10.6 PROTOCOL AMENDMENT HISTORY

Prior amendments are listed below in order of occurrence. Current amendment is provided in section above table of contents.

Original	10 May 2022
----------	-------------

Amendment 1.0, 15 June 2022

Overall Rationale for the Amendment:

Changes are shown in order of appearance.

Section # and Name	Description of Change	Brief Rationale
1.3 SoA	
 • Add vital signs measurements on Day 1 at 15 and 30 minutes postdose 	
 • Per request of the IRB
5.1 Inclusion criteria 10.1.1 Informed Consent Process	
 • Clarify that legally authorized representative will also sign assent form for cognitively impaired subjects 	
 • Per request of the IRB
Global	
 • Ensure consistency across protocol including typo corrections • Correct formatting and style • Add summary of changes page • Update footer and title page with date/amendment number 	
 • For clarity and consistency

Amendment 2.0, 01 July 2022

Overall Rationale for the Amendment:

Changes are shown in order of appearance.

Section # and Name	Description of Change	Brief Rationale
1.1 Synopsis 1.2 Schema 4 Study Design 9.1 Sample Size Determination	
 • Add 2 sentinel healthy volunteers to cohorts 1-4 • Adjust sample size 	
 • To enhance the safety of participants at each cohort and maintain the blind at the imaging center.
8.1.1	
 • Indicate that visual acuity will be done by Snellen eye chart 	
 • For clarification
10.2 Clinical Laboratory Tests	
 • Replace central laboratory with local laboratory 	
 • For logistical and operational reasons

Section # and Name	Description of Change	Brief Rationale
Global	
 • Ensure consistency across protocol including typo corrections • Correct formatting and style • Move prior amendment to Section 10.6 • Update footer, title page and signature page with date/amendment number 	
 • For clarity and consistency

Amendment 3.0, 26 July 2022

Overall Rationale for the Amendment:

Changes are shown in order of appearance.

Section # and Name	Description of Change	Brief Rationale
Protocol title 1.1 Synopsis 1.2 Schema 1.3 Schedule of Activities 2. Introduction 3 Objectives and Endpoints 4 Study Design 5 Study Population 6 Study Drug 9 Statistical Considerations 10.1.5 Safety Oversight – Safety Monitoring Committee	
 • Remove healthy volunteers participation in the study 	
 • As a safety precaution per FDA request based on preliminary nonclinical finding requiring additional in vitro testing
2.3.1 Known potential risks 6.1.1 Study Drug Description	
 • Add that due to potential phototoxicity, subjects will be instructed to avoid direct sun and wear protective gear for 24 hours after dosing. • Add mutagenicity as a potential risk 	
 • As a safety precaution per FDA request
6.1.1 Study Drug Description	
 • Clarify study drug is a single dose vial not to be shared between subjects. 	
 • To align with the investigator's brochure

Section # and Name	Description of Change	Brief Rationale
Global	
 Update protocol to ensure consistency across protocol Correct formatting and style Move prior amendment to Section 10.6 Update footer, title page and signature page with date/amendment number 	
 For clarity and consistency

Amendment 4.0, 16 September 2022
Overall Rationale for the Amendment:

Changes are shown in order of appearance.

Section # and Name	Description of Change	Brief Rationale
1.3 Schedule of Activities 8.1.2 Retinal fundus fluorescence (FF) imaging	
 Clarify timing of when assessments will be performed 	
 For clarity
1.1 Synopsis 4.1 Study design 9.1 Sample Size Determination	
 Indicate that approximately 12 ALS subjects will be enrolled 	
 For clarity
10.2 Clinical Laboratory Tests	
 Delete urine test for drugs of abuse 	
 This assessment is not conducted in the studied subject population
Global	
 Update protocol to ensure consistency across protocol Correct formatting and style Move prior amendment to Section 10.6 Update footer, title page and signature page with date/amendment number 	
 For clarity and consistency

1 INTRODUCTION

This statistical analysis plan (SAP) provides a comprehensive and detailed description of analyses and reporting of data for study protocol AMDX-2011P-101P Version 1.0-Master containing sub-study protocols: AMDX-2011P-001 Version 1.0 and AMDX-2011P-101 Version 5.0, Amendment 5.0. The purpose of the SAP is to ensure the credibility of the study findings by pre-specifying the statistical approaches to the analysis of study data prior to data base lock.

1.1 Changes from Protocol

The visit window for analysis was changed from +2 days to +6 days.

2 STUDY OBJECTIVES

2.1 Primary Objective

The primary study objective is:

- to assess safety and tolerability of single IV dose of AMDX-2011P in subjects with neurodegenerative diseases (Parkinson's disease, Amyotrophic Lateral Sclerosis (ALS), multiple system atrophy (MSA), and Cerebral Amyloid Angiography (CAA)).

2.2 Secondary Objective

The secondary study objectives are:

- to assess the ability of AMDX-2011P to identify α -syn in retina of subjects with Parkinson's disease and MSA.
- to assess the ability of AMDX-2011P to identify TDP-43 in retina of subjects with ALS.
- to assess the ability of AMDX-2011P to identify Amyloid Beta in the retina of CAA subjects.
- to characterize the PK profile of AMDX-2011P and AMDX-2011 following administration of a single IV dose of AMDX-2011P in subjects with neurodegenerative diseases (Parkinson's Disease, ALS, MSA, and CAA).

3 STUDY DESIGN

This is a Phase I PROBE basket design study to evaluate safety, tolerability, and the ability of AMDX-2011P to detect amyloid deposits, α -syn, TDP-43, and Amyloid Beta through retinal examination, as well as PK of single bolus IV of AMDX-2011P in subjects with Parkinson's disease, Amyotrophic Lateral Sclerosis (ALS), Cerebral Amyloid Angiopathy (CAA), and multiple system atrophy (MSA). The study contains two sub-studies under separate protocols.

List of sub-studies included in Master Protocol Basket Design:

Study Protocol	Study Population	Protocol Appendix for further details	Dose Levels	Number of Cohorts	Subjects Per Cohort

Study AMDX-2011P-001 Version 1.0	Cerebral Amyloid Angiopathy (CAA)	Section 7.1	50 mg (2mL), 100 mg, 150 or 200 mg (tentative), Cohort 4 (TBD)	4	3-5
Study AMDX-2011P-101 Version 5.0, Amendment 5.0	Amyotrophic Lateral (ALS) / Parkinson's Disease, Multiple System Atrophy (MSA)	Section 7.2	25 mg (1mL), 50 mg (2mL), 100 mg (4 mL), 150 mg or 200 mg (6-8 mL)	4	3-9 for cohorts 1-2, 12 for cohorts 3-4

Approximately 9 subjects will be enrolled in each of the ALS and MSA studies. Additional subjects may be enrolled into any cohort per DSMB recommendation for CAA sub-study and all sub-study cohorts will include 1 sentinel subject who will be observed for 8 hours and evaluated at 24 hours for safety before enrolling the remaining subjects into that cohort. Tentative doses will be determined and confirmed by DSMB based on emerging data from prior cohorts. Additional cohorts may be explored per DSMB recommendations.

3.1 Sample Size Considerations

A total sample size of approximately 36 subjects and assuming approximately 10% subjects are false negative, the sub-study will provide test sensitivity of at least 0.8 for each individual subject population and the pooled populations in protocol AMDX-2011P-101 Version 5.0, Amendment 5.0. The study will enroll approximately 36 subjects with confirmed diagnosis of Parkinson's disease, ALS, or MSA; the prevalence of disease is assumed at 0.75 for pooled population and 0.5 for each individual disease population. For the CAA group, a total sample size of up to 20 subjects with confirmed diagnosis of CAA, and assuming approximately 10% subjects are false negative, the sub-study will provide test sensitivity of approximately 0.8 for the target population in protocol AMDX-2011P-001.

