4 STUDY DESIGN

4.1 OVERALL DESIGN

This is a PROBE study designed to evaluate safety, tolerability, and the ability of AMDX-2011P to detect amyloid deposits, α -syn and TDP-43 (collectively called amyloidogenic deposits) through retinal imaging, as well as PK of single bolus IV of AMDX-2011P in subjects with Parkinson's disease, MSA and ALS. Study schema is shown in Section 1.2.

The study will enroll up to 4 dose cohorts, as shown in Table 3:

Table 3 Cohorts and Planned Doses

Cohort	Number of Subjects with neurodegenerative diseases (Parkinson's Disease and/or MSA and/or ALS) ^a	Proposed dose level
1	3-9 ^b	25 mg (1 mL)
2	3-9 ^b	50 mg (2 mL)
3	12 ^b	100 mg ^c (4 mL)
4	12 ^b	150 or 200 mg ^c (6-8 mL)

Abbreviation: ALS, amyotrophic lateral sclerosis; SMC, Safety Monitoring Committee; TBD, to be determined.

a. Additional subjects (from any subject population) may be enrolled into any cohort per SMC discretion.

Approximately 9 ALS subjects will be enrolled in the study. Approximately 9 MSA subjects will be enrolled.

b. All cohorts will include 1 sentinel subject who will be observed for 8 hours and evaluated at 24 hours for safety before enrolling the remaining subjects in that cohort.

c. Tentative dose and will be confirmed by SMC based on emerging data from the prior cohorts; intermediate or higher dose level may also be explored in these cohorts.

A Safety Monitoring Committee (SMC), comprised of the Study Medical Monitor (or designee), neurologists with experience in these diseased populations, an ophthalmologist with retinal imaging expertise, and the Sponsor's clinical and technical representatives, will review safety data throughout the study. The SMC may recommend modifying the duration of observation or timing of study procedures based on safety and other available data from the first cohort. For additional details, refer to Section 10.1.5.

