9 STATISTICAL CONSIDERATIONS

9.1 SAMPLE SIZE DETERMINATION AND STATISTICAL HYPOTHESES

This clinical study is designed to explore safety and preliminary activity of AMDX-2011P. A total sample size of ~36 subjects and assuming approximately 10% subjects are false negative, the study will provide test sensitivity and test specificity of approximately 0.8 for each individual subject population and the pooled populations. The study will enroll up to 36 subjects with confirmed diagnosis of Parkinson's disease, MSA or ALS (approximately 12 subjects); the prevalence of disease is assumed at 0.5 for each individual disease population.

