6 STATISTICAL ANALYSIS METHODS

No formal statistical tests or inference will be performed. All summaries will be presented using descriptive statistics for each cohort, and overall. Data processing, summarization, and analyses will be performed using SAS Version 9.4 or higher. Unless otherwise discussed, continuous variables will be summarized by the number of available data points (N), mean, standard deviation, median, minimum, and maximum. 90% confidence intervals, least-square means, and ratio for geometrics LS means will be displayed when appropriate. The mean, median, minimum, and maximum will be displayed with the same number of decimals as raw data, and the standard deviation will be displayed with two more decimals than raw data. Categorical variables will be summarized by the number and percentage of subjects in each level, where the denominator for each percentage is the number of subjects in the relevant population and specified cohort. Percentages will be displayed to one decimal place and proportions will be displayed to three decimal places. Data listings of all data collected on the eCRF will be presented, sorted by subject number and visit, where applicable.

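### SAP 3.1 and protocol 9.1 say that about 36 subjects will provide a sensitivity of 0.8 in each disease; the figure does not depend on sample size, and 9 ALS or 9 MSA subjects cannot demonstrate it

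*SAP*

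**What the plan says.** SAP 3.1 starts from "A total sample size of approximately 36 subjects and assuming approximately 10% subjects are false negative" and concludes that "the sub-study will provide test sensitivity of at least 0.8 for each individual subject population and the pooled populations". It adds that "the prevalence of disease is assumed at 0.75 for pooled population and 0.5 for each individual disease population". The same paragraph says who is enrolled: "The study will enroll approximately 36 subjects with confirmed diagnosis of Parkinson's disease, ALS, or MSA". For CAA it claims approximately 0.8 from up to 20 subjects, again with about 10% false negatives.

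Protocol 9.1 makes the parallel claim that "the study will provide test sensitivity and test specificity of approximately 0.8 for each individual subject population and the pooled populations", with an assumed prevalence of 0.5 for each disease and no pooled value.

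On group sizes, SAP 3 says "Approximately 9 subjects will be enrolled in each of the ALS and MSA studies", and protocol 4.1 agrees: "Approximately 9 ALS subjects will be enrolled in the study. Approximately 9 MSA subjects will be enrolled". The protocol synopsis and protocol 9.1 give about 12 for ALS. Neither document states a number for Parkinson's disease.

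On intervals, SAP 6 rules out formal tests and inference. Among its rules for continuous variables it says "90% confidence intervals, least-square means, and ratio for geometrics LS means will be displayed when appropriate". SAP 6.8 promises diagnostic summary statistics overall but names no interval, and it defines a false negative per eye, whereas SAP 3.1 counts subjects. Protocol 9.3.1 asks for the sample-size variables for the pooled population and for each disease.

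**The concern.** Sensitivity is a property of the tracer and the reading procedure. The number of subjects determines how precisely it is estimated. The SAP sentence presents a performance floor as something the design delivers, and says neither how sure one can be of it nor in what sense it holds.

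The risk is in interpretation. A bare 8/9 (88.9%) in ALS would look as if it had met a planned target of 0.8, although the data would be compatible with a sensitivity below 0.6. Conversely, a tracer with a true sensitivity of 0.9 could give 7/9 (77.8%) by chance and look like a failure. Detection in each disease is a secondary objective, so such percentages are likely to be read closely.

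**Working it through.** **Inputs from the documents.** False negatives about 10% of subjects; prevalence 0.5 per disease and 0.75 pooled; total about 36, all with confirmed diagnosis (SAP 3.1). About 9 ALS and 9 MSA (SAP 3, protocol 4.1), or about 12 ALS (protocol synopsis and 9.1). About 20 CAA at most (SAP 3.1). A 90% level (SAP 6, protocol 9.3.1).

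**Assumptions added here.** 36 − 9 − 9 = 18 Parkinson's disease subjects; a 95% level for comparison; exact (Clopper-Pearson) two-sided limits; subjects as the unit; independent subjects.

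**Step 1: reproduce 0.8.** No formula is given. If the 10% is a share of all subjects tested, sensitivity = (prevalence − false-negative share)/prevalence:
- each disease: (0.5 − 0.1)/0.5 = 0.800
- pooled: (0.75 − 0.1)/0.75 = 0.867

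Together these give a value of at least 0.8 in every group. N does not appear, so 10 or 1,000 subjects would give the same figures.

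**Step 2: apply it to the sample enrolled.** Every subject is diseased, so prevalence is 1.0 and sensitivity = (1.0 − 0.1)/1.0 = 0.90. The 0.8 disappears.

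**Step 3: could 0.8 be a lower confidence limit?** At an assumed 0.9, the simple normal limit 0.9 − z√(0.09/n) is, at 95% and 90%:
- n = 36: 0.802 and 0.818
- n = 18: 0.761 and 0.784
- n = 9: 0.704 and 0.736

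That could account for the pooled claim but not for the claim about each disease.

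Exact lower limits when every subject is positive, (α/2)^(1/n):

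| Result | 95% | 90% |
|---|---|---|
| 9/9 | 0.664 | 0.717 |
| 12/12 | 0.735 | 0.779 |
| 18/18 | 0.815 | 0.847 |

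An all-positive group needs 17 subjects (95%) or 14 (90%) for the exact limit to reach 0.8.

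**Step 4: could 0.8 be an assured observed value?** If true sensitivity is 0.9:
- n = 9, at least 8 positive: 9 × 0.9⁸ × 0.1 + 0.9⁹ = 0.387 + 0.387 = 0.775
- n = 12, at least 10 positive: 0.889
- n = 18, at least 15 positive: 0.902
- n = 36, at least 29 positive: 0.976
- all three diseases, 18/9/9: 0.902 × 0.775 × 0.775 = 0.54
- all three diseases, 12/12/12: 0.889³ = 0.70

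**Step 5: precision the design does give.** Exact 90% intervals at about 10% false negatives:

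| Group | Result | 90% interval |
|---|---|---|
| ALS or MSA, 9 | 8/9 | 0.57–0.99 |
| Parkinson's disease, 18 | 16/18 | 0.69–0.98 |
| Pooled, 36 | 32/36 | 0.76–0.96 |
| CAA, 20 | 18/20 | 0.72–0.98 |

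**The case against.** The study is exploratory. Its primary aim is safety, SAP 6 excludes inference, and SAP 3.1 never calls 0.8 a confidence bound. On a plain reading 0.8 is a point value, it follows from the stated inputs, and 9/9 (1.00) or 8/9 (0.889) would satisfy it. All of this is true. It means that a reader should not infer that 9 subjects could never show a sensitivity of 0.8; the shortfall appears only when 0.8 is treated as something to be demonstrated with confidence. But on the point-value reading the sentence only restates assumptions and gives no reason for choosing 36, and those assumptions do not fit the sample.

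A reader might also infer that no single disease can reach 0.8 as a bound. That goes too far: 18/18 in Parkinson's disease gives 0.815 at 95%. With 12 ALS subjects, 12/12 falls short on the exact 90% limit (0.779) but not on the Wilson limit (0.816), so that result depends on the method.

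A third inference is that the SAP quietly tightened the protocol's target from approximately to at least 0.8. SAP 1.1 does not list the change, but it has an innocent explanation: the SAP adds the pooled prevalence of 0.75, which yields 0.867 beside 0.80.

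Finally, nine subjects may contribute 18 eyes, and SAP 6.8 counts eyes. Treating 18/18 eyes as independent gives 0.815 (95%), but two eyes of one subject are correlated, so that limit is too high. The committee may also add subjects, but no larger number is planned.

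**Conclusion.** The point stands in this form. The sample-size statement claims something that a sample size cannot confer. Its 0.8 comes from prevalences that contradict the enrolment of confirmed cases only, and the planned 9 ALS and 9 MSA subjects cannot demonstrate 0.8 at 90% or 95% confidence, even with every subject positive (exact lower limit 0.72 or 0.66). Nor is an observed 0.8 assured: the chance is 0.77 per group of 9, and 0.54 for all three diseases, at a true sensitivity of 0.9.

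These figures rest on subjects as the unit, on exact limits, and on the derived 18 Parkinson's disease subjects. The prevalence formula is inferred from the inputs, since neither document states one.

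This should be fixed, but it is not critical. Activity is a secondary, descriptive endpoint, and no dose, stopping or success rule is tied to 0.8.

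**What to change.** - **SAP 3.1 and protocol 9.1:** delete the claims that the sample will provide a given sensitivity, together with the 0.5 and 0.75 prevalence inputs. State the expected precision at about 10% false negatives, using the exact 90% intervals in the last table of the working. Restate the CAA sentence in the same way. Settle whether ALS is 9 or 12, so that the quoted interval matches the planned number.
- **SAP 6.8:** report each sensitivity, per disease and pooled, as n/N with its exact 90% interval at subject level, and state how the two eyes combine into one subject result. If the per-eye definition is kept, use an interval that allows for correlation between a subject's eyes.
- **SAP 1.1:** list the change if the protocol is not amended at the same time.

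No extra subjects and no design change are needed. The cost is wording in two documents and a stated figure that looks less favourable.
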